Clinical Study Protocol

Dotarem® for Myocardial Perfusion Cardiovascular Magnetic Resonance

Principal Investigators: U. [name]

Medical University of South Carolina
Department of Radiology and Radiological Science
[name]
[name]

CONFIDENTIALITY STATEMENT

This document is the confidential property of Medical University of South Carolina, Radiology Department. No Part of it may be transmitted, reproduced, published or used by other persons without the permission of the Principal Investigator.

Dotarem® Evaluation for Myocardial Perfusion Cardiovascular Magnetic Resonance

Table of Contents

A. SPECIFIC AIMS	3
B. BACKGROUND AND SIGNIFICANCE	3
C. PRELIMINARY STUDIES	3
D. RESEARCH DESIGN AND METHODS (including data analysis)	4
D.1 Image acquisition	4
D.2 Image analysis	5
D.3 Statistical Methods / Sample Size Justification	5
E. PROTECTION OF HUMAN SUBJECTS	5
E.1 RISK TO THE SUBJECTS	5
E.1.a Human Subject Involvement and Characteristics	5
E.1.b Sources of Materials	7
E.1.c Potential Risks	7
E.2 ADEQUACY OF PROTECTION AGAINST RISKS	8
E.2.a Recruitment and Informed Consent	8
E.2.b Protection against Risk	9
E.3 POTENTIAL BENEFITS OF THE PROPOSED RESEARCH TO THE SUBJECTS AND OTHERS	9
E.4 IMPORTANCE OF THE KNOWLEDGE TO BE GAINED	9
E.5 SUBJECT SAFETY AND MINIMIZING RISKS (Data and Safety Monitoring Plan)	10
F. FACILITIES AVAILABLE	10
G. REFERENCES	10

A. SPECIFIC AIMS

The overall goal of this study is to investigate the signal intensity and relaxation rate characteristics of gadoterate meglumine (Dotarem, Guerbet, USA) enhanced myocardium during rest and stress perfusion cardiovascular magnetic resonance (CMR) compared to gadobutrol (Gadavist) to prove that Dotarem provides constantly high myocardial relaxation necessary for accurate quantitative perfusion evaluation. Within this overall goal, the following specific aims will be pursued:

- **Aim 1:** To test the hypothesis that the signal intensity enhancement during Dotarem myocardial stress/rest perfusion is relatively constant, providing linear and stable enhancement in the myocardium, and is not inferior compared to gadobutrol (Gadavist).
- **Aim 2:** To test the hypothesis that the relaxation rate enhancement during Dotarem myocardial rest perfusion is uniform in the myocardium.

B. BACKGROUND AND SIGNIFICANCE

Stress perfusion imaging is indicated in symptomatic patients suspected of coronary artery disease (CAD) with low or intermediate cardiovascular risk and typical/atypical chest pain or angina-equivalent symptoms, as well as in asymptomatic patients with high cardiovascular risk profiles, such as diabetics, or in patients with known CAD during follow-up.¹ Myocardial perfusion by CMR was introduced approximately two decades ago.² Compared with SPECT, which uses a radioisotope that is actively taken up by the myocytes to depict myocardial perfusion, CMR evaluates the first pass of an extracellular contrast agent (CA) within the myocardium. Whereas the stress protocol used for both methods is similar, CMR offers the benefit of superior spatial and temporal resolution, and SPECT is associated with the negative effects of exposure to ionizing radiation.^{3, 4} Although, several studies proved that stress perfusion CMR outperforms stress perfusion SPECT⁵⁻⁷, the quantitative evaluation of myocardial blood flow by CMR is still a challenging topic due to, for example, the non-linear signal intensity changes and the different relaxation rate enhancements caused by the various gadolinium-based CAs⁸⁻¹⁰, representing a major limitation to the widespread use of the technique in clinical practice.

Dotarem, a macrocyclic agent with fast clearance kinetics, has the highest thermodynamic stability among the currently approved clinical contrast agents.¹¹ This high stability is due to its molecular structure, which provides a significantly reduced dissociation rate (i.e. Release of free gadolinium ions) compared to other agents.¹¹ While the *in vitro* relaxivity ($3.4 \text{ mm}^{-1}\text{s}^{-1}$)¹² of Dotarem is comparable to other agents, we suggest that its high stability and extremely low dissociation rate provide constant signal intensity and relaxation rate enhancement during myocardial perfusion CMR, improving the accuracy and reliability of quantitative perfusion analysis.

The efficacy of Dotarem enhanced late gadolinium enhancement (LGE) imaging has been investigated and compared to gadobutrol (Gadavist, Bayer, Germany) to visualize and quantify myocardial scar.¹³ However, a similar comparison for the assessment of myocardial ischemia by CMR myocardial perfusion – an even more crucial step in a clinical CMR protocol – would further strengthen the value of Dotarem in cardiovascular imaging. While LGE is able to visualize irreversible myocardial injury, myocardial perfusion imaging has the ability to depict reversible ischemia that can potentially be treated by coronary intervention.

C. PRELIMINARY STUDIES

Our research group consists of clinical and research faculty who have extensive experience and a substantial publication record related to contrast enhanced cardiac MRI and contrast agent characterization.¹⁴⁻¹⁸ In a previous research project, our team developed an image analysis technique (detailed in Section D) that we will use in Aim 2 to investigate the relaxation profile of Dotarem.¹⁶

D. RESEARCH DESIGN AND METHODS (INCLUDING DATA ANALYSIS)

D.1 IMAGE ACQUISITION

This prospective study will include a total of 90 patients (Aim 1 + Aim 2) who present to the MUSC Radiology Department for a clinically indicated cardiac MRI scan over a 2-year period. Patients will be imaged using a state of the art 1.5T scanner (MAGNETOM Avanto, Siemens Healthcare, Erlangen, Germany) system.

Aim 1: In this specific aim, a total of **60 patients** referred for a clinically indicated stress myocardial perfusion MRI scan out of concern of suspected myocardial ischemia will be included. Patients will be scanned using a **standard clinical contrast-enhanced stress perfusion protocol** (regadenoson 0.4mg bolus) detailed in Figure 1. Patients will be randomized into two groups prior to patient consenting: **Group 1 (n=30)** will receive the **clinically approved gadoterate meglumine** (Dotarem, 0.1mmol/kg) as contrast agent for their clinical perfusion study, while **Group 2 (n=30)** will receive the **clinically approved gadobutrol** (Gadavist, 0.1mmol/kg) as contrast agent. The contrast agents will be administered at a flow rate of 5.0 ml/s for both groups. In this study aim, all imaging protocols will comply with standard of care and only the perfusion data will be post-processed and analyzed.

Aim 2: In this specific aim, a total of **30 patients** referred for a clinically indicated contrast enhanced cardiac MRI will be included. These patients will undergo a **clinical viability cardiac MRI protocol** with the administration of **gadoterate meglumine** (Dotarem, 0.1mmol/kg), except that a **prototype MRI T1 mapping pulse sequence** will be used to acquire equilibrium T1 maps during the first pass of the contrast agent. This first pass perfusion step will be performed in rest, no stress agent will be administered. The rest perfusion acquisition is part of the standard protocol, however, we will use this prototype pulse sequence for research purposes.

[figure not shown]

Figure 1 – MRI protocols

D.2 IMAGE ANALYSIS

In Aim 1, we will generate signal intensity-time curves from the perfusion data and evaluate the characteristics of signal intensity changes and absolute myocardial blood flow using the MASS Research Software (LUMC, Leiden, Netherlands). The signal characteristics will be compared between the two contrast groups. Image quality will also be subjectively rated by multiple independent observers.

In Aim 2, we will generate equilibrium T1 maps based on the pre-contrast T1 and repeated inversion recovery images during the perfusion of the CA. This technique allows the calculation of the post-contrast T1 at every phase during the first-pass perfusion of the CA. The uniformity of T1 and R1 (inverse T1) will be evaluated using the MASS Research Software.

D.3 STATISTICAL METHODS / SAMPLE SIZE JUSTIFICATION

All analyses and graphs will be performed by using commercially available software (MedCalc version 12.7.2; SPSS version 21). Descriptive statistics will be provided as mean \pm standard deviation (SD) for continuous variables and absolute and relative frequencies for categorical variables. Normal data distribution will be assessed with a Kolmogorov-Smirnov test. For each group, comparisons of patient characteristics will be performed by using the χ^2 test for categorical variables and t-test or Mann-Whitney-U-test for continuous variables as appropriate. Subjective image quality scores will be compared using the χ^2 test with the Yates continuity correction for categorical variables and inter-observer agreement for image quality will be calculated using Cohen kappa statistics and interpreted as follows: ≤ 0.20 slight or poor agreement, $0.20-0.40$ fair agreement, $0.40-0.80$ moderate agreement, ≥ 0.80 excellent agreement.

E. PROTECTION OF HUMAN SUBJECTS

E.1 RISK TO THE SUBJECTS

E.1.a Human Subject Involvement and Characteristics

Aim 1

Inclusion criteria:

To be eligible for the study: (All answers must be “YES” for subject to be eligible.)

1. Subject must be referred for a clinically indicated contrast-enhanced stress myocardial perfusion MRI scan out of concern of suspected myocardial ischemia.
2. Subject must be older than 18 years of age.
3. Subject must provide written informed consent prior to any study-related procedures being performed.
4. Subject must be willing to comply with all clinical study procedures.

Exclusion Criteria:

The presence of the following excludes subjects from the study: (All answers must be “NO” for subject to be eligible.)

1. Subject is a pregnant or nursing female. Exclude the possibility of pregnancy:
 - By testing (serum or urine beta HCG) within 24 hours before study date, or
 - By surgical sterilization, or
 - Post-menopausal, with minimum one (1) year history without menses.
2. Subject has an implanted cardiac pacemaker or implantable defibrillator.
3. Subject has a ferromagnetic vascular clip.
4. Subject has a neurostimulation system (e.g. TENS-Unit).

5. Subject has any type of cochlear implant.
6. Subject has ocular foreign body (e.g. metal shavings).
7. Subject carries any implanted device (e.g. insulin pump, drug infusion device).
8. Subject has shrapnel, bullet, or other type of metal fragments within the body.
9. Subject has an acute psychiatric disorder or is cognitively impaired.
10. Subject is using or is dependent on substances of abuse.
11. Subject is unwilling to comply with the requirements of the protocol.
12. Subject is in acute unstable condition.
13. Subject has an allergy against gadolinium based contrast agents or pharmaceutical stressors used in this study.
14. Subject has impaired renal function (creatinine > 1.5 mg/dl).
15. Subject presenting with acute coronary syndrome.
16. Positive cardiac enzymes positive troponin, CK-MB, or myosin
17. ST-elevations, new transient ST changes greater than 0.05mV or T- wave inversions with symptoms

Aim 2

Inclusion criteria:

To be eligible for the study: (All answers must be “**YES**” for subject to be eligible.)

1. Subject must be referred for a clinically indicated contrast-enhanced stress myocardial perfusion MRI scan out of concern of suspected myocardial ischemia.
2. Subject must be older than 18 years of age.
3. Subject must provide written informed consent prior to any study-related procedures being performed.
4. Subject must be willing to comply with all clinical study procedures.

Exclusion Criteria:

The presence of the following excludes subjects from the study: (All answers must be “**NO**” for subject to be eligible.)

1. Subject is a pregnant or nursing female. Exclude the possibility of pregnancy:
 - By testing (serum or urine beta HCG) within 24 hours before study date, or
 - By surgical sterilization, or
 - Post-menopausal, with minimum one (1) year history without menses.
2. Subject has an implanted cardiac pacemaker or implantable defibrillator.
3. Subject has a ferromagnetic vascular clip.
4. Subject has a neurostimulation system (e.g. TENS-Unit).
5. Subject has any type of cochlear implant.
6. Subject has ocular foreign body (e.g. metal shavings).
7. Subject carries any implanted device (e.g. insulin pump, drug infusion device).
8. Subject has shrapnel, bullet, or other type of metal fragments within the body.
9. Subject has an acute psychiatric disorder or is cognitively impaired.
10. Subject is using or is dependent on substances of abuse.
11. Subject is unwilling to comply with the requirements of the protocol.
12. Subject is in acute unstable condition.
13. Subject has an allergy against gadolinium based contrast agents used in this study.
14. Subject has impaired renal function (creatinine > 1.5 mg/dl).

There will not be any eligibility criteria for any subpopulations. In addition, there will not be any targeted involvement of special classes of subjects, such as fetuses, neonates, pregnant women,

children, prisoners, institutionalized individuals, or others who may be considered vulnerable populations. All race and ethnicities and both genders will be considered for inclusion into the study. Subjects under the age of 18 will not be considered for inclusion into this study.

Targeted/Planned Enrollment Table

Total Planned Enrollment: 90 (Aims 1 and 2 combined)

Table 1: Targeted/planned enrollment (number of subjects).			
Ethnic Category	Sex/Gender		
	Females	Males	Total
Hispanic or Latino	3	3	6
Not Hispanic or Latino	42	42	90
Ethnic Category: Total of All Subjects	90		
Racial Categories			
American Indian/Alaska Native	0	0	0
Asian	1	1	2
Native Hawaiian or Other Pacific Islander	0	0	0
Black or African American	12	12	24
White	32	32	64
Racial Categories: Total of All Subjects	45	45	90

E.1.b Sources of Materials

The research materials that will be obtained from living human subjects are: the MR images, report, injection report, progress notes, medication records, vital signs, medical history and demographics, and all other applicable clinical information.

The Principal Investigator, Sub-Investigator(s) and the Study Coordinator(s) will be the only personnel who will have access to subject identities, with the exception of any regulatory personnel (MUSC IRB auditors, etc.). All subject identities will be removed prior to publication.

Contrast and Drug Management

Contrast agents (Dotarem and Gadavist) and stress agent (Regadenoson) will be ordered and dispensed from the MUSC inpatient pharmacy per clinical protocol.

E.1.c Potential Risks

Vein puncture

Patients could experience bruising, pain, and rare incidence of infection at the vein puncture site. This is like a blood test. This puncture is used to inject the contrast agents. Care will be taken to avoid these possible risks. Skin or vein irritation, fainting, blood clot formation, bleeding at the injection site, or an infection could also occur.

Adverse reactions caused by gadolinium contrast agent

Gadolinium contrast agent will be administered as part of the clinical protocol, independently from the research component of the study. The research protocol will not increase the risk of contrast related adverse reactions in any of the research aims. Despite excluding patients with known history of allergy

to gadolinium-based contrast material, there is a small risk that a patient will have an allergic reaction to contrast medium. In this event, the attending physician supervising the MRI acquisition in the study will administer appropriate care. In patients with pre-existing renal dysfunction, gadolinium-based contrast material may cause further deterioration in renal function. Therefore, patients with decreased renal function (more than 1.50 mg/dL serum creatinine) will be excluded from this study.

Risks from Contrast Agent Extravasation

Although extremely rare, it is possible that an IV needle is not properly located within the vein or becomes dislodged when the patient lies down on the examination table. When contrast material is injected, it may then leak into the surrounding tissue. This can be painful and in very few instances has been reported to cause pressure on underlying nerves or vessels that needs to be surgically relieved. Usually, however, a contrast media extravasation is noticed early on by the personnel monitoring the procedure. However, even if a full dose of contrast material is injected in the tissue surrounding a vein, permanent damage is extremely unlikely. Usually the contrast material is fully absorbed by the body within a day without any harmful effect. In addition, in our department we use the latest automated contrast media injector generation, which also comprises of an automated extravasation detection device attached to the arm of the patient. Since the implementation of this device we have not experienced any major extravasation of contrast material.

Adverse reactions caused by stress agent administration

The following reactions are listed as warnings and precautions when using regadenoson (Lexiscan): Myocardial ischemia, sinoatrial and atrioventricular nodal block, hypotension, bronchoconstriction. The following adverse reactions associated with regadenoson are considered transient and are listed in the package insert: dyspnea or urge to breathe deeply, headache, flushing, chest discomfort, angina pectoris or ST segment depression, lightheadedness/dizziness, chest pain, nausea, abdominal discomfort, impaired taste, feeling hot. In addition, dyspnea can occur during stress myocardial perfusion imaging with associated arrhythmias such as hypoxia induced bundle branch block. The first signs of these rare side effects will cause the termination of the examination. Note, that stress agent will not be administered for research purposes.

Risk of metal objects in the body

Patients may suffer bodily harm in the course of the MRA examination from having metal objects in their clothing, from metal implants (e.g. pacemaker, implanted defibrillator, cochlear implants, cerebral aneurysm clips), or any other metal within the body (shrapnel, bullet or metal fragments). Before patients undergo the procedure, they will be prompted to take out any metal objects. Patients will be asked a series of detailed questions about any metal that they may have their body.

Acquisition of patient information

The risks associated with gathering this information are believed to be very low. This information will be stored on a password-protected computer and network server and in a locked office (ART Cardiac Imaging Research Office). The data from this study will be accessible only to the team of researchers from this application.

E.2 ADEQUACY OF PROTECTION AGAINST RISKS

E.2.a Recruitment and Informed Consent

Patients who have been referred for a stress myocardial perfusion MRI (Aim 1) or myocardial viability MRI (Aim 2) as part of a standard clinical evaluation determined by the treating physician(s) will be eligible for the study and recruited from the MUSC MRI schedule. The MRI technologist or member of the nursing staff will speak with potential subjects to ensure their willingness to be approached by a member of the research team. Willing patients will be approached and will undergo the informed

consent process. Consented subjects will undergo their clinically indicated MRI using the standard stress protocol (Aim 1) or the modified viability protocol (Aim 2).

Patients will be screened by approved study personnel from the MUSC MRI schedule under a HIPAA waiver. Study eligibility determination and study enrollment will be assessed and performed by and investigator in concert with a study coordinator delegated by the PI and approved by the IRB as being authorized to obtain informed consent.

The PI, Sub-I(s) or the Study Coordinator(s) will obtain informed consent prior to enrollment into the study. The subject will be taken to a quiet/private area (which may include the scanning room, the patient bays or other private areas) and the study purpose, procedures, duration, risks/discomforts, benefits, alternatives, new information procedures and privacy statements will be explained to the subject.

The subject will be asked to verbally repeat pertinent study information to ensure subject understands the nature of the research. Subjects will be provided the opportunity to ask any questions they may have. Consent will be documented in the currently IRB approved version of the informed consent and will be signed and dated by the person obtaining informed consent and the subject.

E.2.b Protection against Risk

To minimize the risk of post-contrast nephropathy, patients with decreased renal function (creatinine >1.5 mg/dL) will not be eligible for this study. To minimize the risk of allergic reactions to gadolinium contrast material, patients with a history of allergic reactions to gadolinium contrast material will also be excluded.

All subjects' medical records will be confined in the usual medical health information office according to their policies and procedures. Each staff member that has approved access to electronic medical records will be given their own password and will be instructed not to reveal that password to anyone else. In addition, those copies of subject information utilized for the research protocol will be kept locked in the Radiology Research suite (ART 2244) in a research specific folder that will identify the subject on the outside of the folder only by initials, subject code (subsequent subject identifiers, i.e. 001, 002, 003, etc., this number will not be able to identify the subject), protocol name, and IRB study number (Pro #). Any data that are used in publication, analyses, etc. will not identify the subject by name, etc. Subjects will be monitored in clinic as per clinical standard practice for any possible side effects and treated as indicated.

E.3 POTENTIAL BENEFITS OF THE PROPOSED RESEARCH TO THE SUBJECTS AND OTHERS

The subjects whose data, documents, and records will be reviewed are not likely to receive any benefit from the proposed research. However, the quantitative and qualitative evaluation of myocardial perfusion has an important role in patient diagnosis, therapy and prognosis. The improved and more reliable detection of myocardial perfusion defects may provide faster diagnosis and better patient management, as well as avoid unnecessary tests (including invasive procedures and radiation exposure). As of today, Dotarem is the only gadolinium-based contrast agent without any reported nephrogenic systemic fibrosis case. Broadening the clinical use of Dotarem towards the cardiac MRI field would provide substantial benefit to patients, especially those who suffer from pre-existing renal disease.

E. 4 IMPORTANCE OF THE KNOWLEDGE TO BE GAINED

Clinical stress myocardial perfusion MRI is a contrast enhanced acquisition that requires the administration of gadolinium-based contrast agent. Currently, there is no FDA label exist for such

applications, thus all the clinical contrast-enhanced cardiac MRI scans are performed off-label. This study will further strengthen the evidence that such clinical indication is warranted and will also demonstrate that Dotarem is a suitable agent to provide diagnostics perfusion data.

E.5 SUBJECT SAFETY AND MINIMIZING RISKS (DATA AND SAFETY MONITORING PLAN)

Eligibility in each case will be confirmed by a named investigator. The source data will be collected by an independent technician and/or study coordinator, maintained securely by the PI and checked by the named investigators. Clinical data will be recorded on a Case Report Form (CRF). However, formal monitoring of site records will not be completed as part of the general conduct of the study. Data collected will be authentic, accurate and complete and the study will be conducted in accordance with the currently approved protocol (and any future approved amendments), Good Clinical Practiced (GCP) and all applicable regulatory requirements.

Any event meeting the criteria of an unanticipated problem involving risks to subjects or others will be reported to the MUSC IRB, as required by HRPP 4.7- Unanticipated Problems and Adverse Events Policy and Procedures. Clinical data will not be monitored by a 3rd party (i.e. Contract Research Organization) or sponsor but the results of the study will be written as a paper and may be submitted as abstracts to various conferences. Every effort will be made to ensure patient safety and confidentiality.

F. FACILITIES AVAILABLE

The Radiology department on the 2nd floor of the Ashley River Tower houses the MAGNETOM™ Avanto on which the MRI will occur. Nursing and physician preparation and monitoring of the patient, including the serum creatinine test, will occur in the patient bays of the Radiology department.

G. REFERENCES

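### Aim 2 entry criterion contradicts its viability recruitment, the goal sentence promises relaxation evidence against gadobutrol that is not planned, and the uniformity analysis has no rule for scar

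*Combined protocol and SAP*

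**What the plan says.** **Goal and aims (Section A).** The goal covers signal intensity and relaxation rate at rest and stress, "compared to gadobutrol (Gadavist) to prove that Dotarem provides constantly high myocardial relaxation". Aim 1 concerns signal intensity and non-inferiority to gadobutrol. Aim 2 is to test the hypothesis that "the relaxation rate enhancement during Dotarem myocardial rest perfusion is uniform in the myocardium".

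**Aim 1 (D.1, D.2).** Sixty patients having a stress perfusion scan are randomized 30 to Dotarem and 30 to gadobutrol. In this aim "only the perfusion data will be post-processed and analyzed". The analysis will "evaluate the characteristics of signal intensity changes and absolute myocardial blood flow using the MASS Research Software", with subjective image quality ratings.

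**Aim 2 (D.1, D.2).** Thirty patients "referred for a clinically indicated contrast enhanced cardiac MRI will be included". They follow a viability protocol with Dotarem and a prototype T1 mapping sequence: "This first pass perfusion step will be performed in rest, no stress agent will be administered". On T1, D.2 says: "This technique allows the calculation of the post-contrast T1 at every phase during the first-pass perfusion of the CA". On the endpoint: "The uniformity of T1 and R1 (inverse T1) will be evaluated using the MASS Research Software". Apart from general descriptive statistics and a normality check, D.3 covers patient characteristics, image quality scores and observer agreement.

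**Aim 2 eligibility.** Inclusion criterion 1 in E.1.a requires referral for a stress perfusion scan for suspected ischemia, and every inclusion answer must be yes. E.2.a recruits Aim 2 from patients referred for viability MRI and scans them with a modified viability protocol.

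**The concern.** Three things do not fit together.

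1. The entry criterion for Aim 2 names a different referral from the one the recruitment section uses. Applied as written, it turns away patients whom the plan means to enrol. Ignored in practice, it makes them protocol deviations.
2. The goal sentence announces a comparative conclusion about relaxation that the planned data cannot give. A report written to that sentence would either overclaim from signal intensity or rest on a single-agent series.
3. Aim 2 attributes uniformity to the agent, but its patients are referred for viability and may have scar. With disease left in and no rule for it, a non-uniform result could reflect the patients rather than Dotarem.

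**Working it through.** **Step 1. Referral for Aim 2, side by side.**

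| Place | Referral or protocol for Aim 2 |
|---|---|
| D.1 | Contrast-enhanced cardiac MRI; viability protocol; rest only, no stress agent |
| E.1.a, inclusion 1 | Stress perfusion scan for suspected ischemia |
| E.2.a | Viability MRI; modified viability protocol |

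Criterion 1 for Aim 2 repeats the Aim 1 criterion word for word. Aim 2 exclusion 13, by contrast, leaves out the stress agents named in the Aim 1 version. A patient referred only for viability meets D.1 and E.2.a but fails E.1.a. A patient referred only for stress perfusion passes E.1.a but is outside the group that E.2.a recruits for Aim 2.

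**Step 2. Where R1 is planned.** The total checks: 30 + 30 + 30 = 90.

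| Group | n | Condition | R1 planned in the text |
|---|---|---|---|
| Aim 1, Dotarem | 30 | stress protocol | no |
| Aim 1, gadobutrol | 30 | stress protocol | no |
| Aim 2, Dotarem | 30 | rest | yes |

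So R1 is planned in 30 of 90 patients, in 0 of 30 on gadobutrol and in 0 under stress. Figure 1 (MRI protocols) is not shown, so a sequence listed only there cannot be ruled out, but D.2 assigns no T1/R1 analysis to Aim 1. Signal intensity cannot simply stand in for R1, because Section B itself names non-linear signal changes as an obstacle to quantification.

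**Step 3. Disease and uniformity (illustration, assumed inputs).** The protocol gives no segment model or R1 variability. Suppose the agent is perfectly uniform, and a fraction f of 16 segments has R1 enhancement lower by a proportion r. Then mean = 1 − f·r, SD = r·√(f(1 − f)) with divisor 16, and CV = SD/mean.

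- f = 4/16, r = 0.3: mean 0.925, SD 0.1299, CV 14.0%.
- f = 2/16, r = 0.2: mean 0.975, SD 0.0661, CV 6.8%.
- f = 6/16, r = 0.5: mean 0.8125, SD 0.2421, CV 29.8%.

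Over this assumed range, regional disease alone gives a CV of about 7% to 30%.

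**Step 4. Phase (illustration, assumed inputs).** T1 is available at every phase, but no phase or summary across phases is chosen for the endpoint. Take 16 segments with identical curves s^a·exp(a(1 − s)), where s = t/(time to peak), a = 2, time to peak 8 s and arrival delays with SD 0.5 s. The across-segment CV is about 19% at half-peak upslope, 4% at 75% of time to peak, 0.4% at peak and 4% at 1.5 times time to peak. It is a little over 2% for the average over 0 to 16 s. The first and third of these are near-extremes.

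**Step 5. What 30 patients can estimate.** The 95% CI half-width for a mean per-patient index is t(0.975, n − 1)/√n between-patient SDs. For n = 30 this is 2.045/5.477 = 0.37. For 20 evaluable patients it is 2.093/4.472 = 0.47. An estimate with an interval is therefore feasible. A pass or fail conclusion is not, because no acceptance limit is set.

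**The case against.** The strongest reply is that the goal sentence is an umbrella. Section A places the two aims under it: stress, gadobutrol and signal intensity belong to Aim 1, and relaxation at rest to Aim 2. No planned analysis claims an R1 contrast with gadobutrol. That is right. A reader might infer that the aims themselves do not match the design, but the documents do not support this; the mismatch lies in the goal sentence, and the remedy there is wording.

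It is also fair to say that the unnamed phase, segment model and statistic are mostly missing detail. A reader might take the contrast between half-upslope and peak in Step 4 as the size of the problem in this trial. It is not: the inputs are assumed, and intermediate phases give about 4%.

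A reader might also note that Aim 1 has three more exclusions than Aim 2 and infer that the shorter list lets scar in. Those three concern acute coronary syndrome, cardiac enzymes and ST/T changes, which are acute presentations. Neither list excludes chronic scar, so the difference in length shows nothing about it.

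Finally, LGE-free segments do not isolate the agent. Resting hypoperfusion without scar, normal flow heterogeneity and measurement noise remain. This limits what the remedy can claim, but not the case for reporting both summaries.

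What stands is the eligibility conflict, the unsupported relaxation claim in the goal sentence, and the absence of any rule for scar.

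**Conclusion.** The point holds in three limited parts, and the plan should be changed.

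- **Eligibility:** a direct contradiction between E.1.a and D.1/E.2.a. Followed literally, it bars every patient referred only for viability from Aim 2. The documents do not give the share of such patients, and this review takes no position on which referral rule is right.
- **Goal sentence:** for relaxation, its comparison with gadobutrol and its stress component have no planned data. This rests on the text alone, since Figure 1 is not shown.
- **Uniformity:** the result as planned can mix disease with agent. The direction follows from the design; the size is unknown. The 7% to 30% range is an illustration on assumed inputs, not an estimate for this trial.

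A reader might conclude that Aim 2 is worthless or that Aim 1 is undermined. Neither follows. Aim 2 can describe Dotarem R1 enhancement at rest with usable precision, and nothing here touches the Aim 1 comparison of signal intensity and blood flow.

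**What to change.** 1. **Eligibility.** Reconcile Aim 2 inclusion criterion 1 in E.1.a with D.1 and E.2.a, so that all three name the same referral.
2. **Section A.** Limit the gadobutrol and stress comparison to Aim 1 signal intensity and blood flow. Describe Aim 2 as estimating Dotarem R1 enhancement at rest, and replace its hypothesis-test wording, since no acceptance limit is set. Remove the word *prove* for relaxation.
3. **D.2/D.3.** Define R1 enhancement as post-contrast minus pre-contrast R1. Fix in advance a segment model that fits the slices acquired, and one phase or one summary across phases, with the reason for the choice. (In the Step 4 model the peak is the phase least sensitive to arrival delay, and Section B speaks of constancy during perfusion.) For each patient compute the mean R1 enhancement and its across-segment CV, then report the average of each over patients with a 95% CI. Do this for all segments and, if LGE is acquired, also for LGE-free segments, with LGE read blind to R1. State that the second summary reduces but does not remove confounding by disease.

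**Cost.** Wording, a few lines of analysis plan and one blinded LGE read. No scan is added if LGE is already in the viability protocol, which is an assumption because Figure 1 is not shown. The downsides are a narrower stated goal, a little more analysis and fewer segments in the LGE-free summary.
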